1.7 Privacy

All data obtained from study participants will be coded and not passed on to other people. Personal data and personal details are stored in paper form in a locked filing cabinet. The head of the research laboratory and at the same time the head of the study has access here, and the administration of the documents also falls within his area of responsibility.

All digital data is encrypted and encoded. No conclusions can be drawn about individuals. The digital data is stored on internal computers, archived and not released to outsiders.

Employees involved in data processing have no insight into the personal data and the coding of it.

1.8 Other committees or institutes involved

The study is being conducted in the research laboratory at the University of Applied Sciences and Arts Southern Switzerland, Physiotherapy Graubünden, [name], Switzerland.

The test products and measuring equipment are all located in this room and therefore all measurements can be carried out at the same location. The room offers enough space.

At present, no further studies with this arrangement are taking place in this experimental laboratory. During this period, no studies will take place in our laboratory.

No other institutes and committees are involved in this study or in the approval or monitoring of the study.

SUPSI

2 ETHNIC & REGULATORY ASPECTS

2.1 Study Registration

The implementation of the present study is the responsibility of the Cantonal Ethics Committee Zurich. An application for admission is submitted. Any further conditions of the responsible ethics committee must be implemented in the study protocol.

When the study protocol is submitted to the Cantonal Ethics Committee in Zurich, the study is also registered with the Swiss Coordination Office for Research on Human Subjects. In addition, the study will be registered in a WHO-recognized primary registry (clinicaltrials.gov).

2.2 Categorization of the study

The study is categorized as another clinical trial of risk category A (ClinO, Art. 20). The subjects are taken to terrestrial and simulated altitudes. Neither tissue samples nor other invasive methods are performed. The simulated height is carried out with a CE certified device according to the instructions for use.

2.3 Competent Ethics Committee (CEC)

Human research in the Canton of Graubünden falls under the remit of the Cantonal Ethics Commission Zurich. Changes to the study protocol are not permitted without the prior consent of the CEC, except for the immediate elimination of obvious hazards to the participants. According to chap. 2.10 to the CEC.

An early termination or interruption of the study must be reported to the CEC within 15 days, and the regular end within 90 days. The final report must be submitted within one year of the end of the programme. Corrections are to be reported in accordance with Chapter 2.10.

2.4 Competent Authorities (CA)

The present study falls under the remit of the Cantonal Ethics Committee Zurich. Obligations and deadlines can be found in the previous point.

2.5 Ethical Leadership of the Study

The study will be conducted in accordance with this protocol and the current version of the Helsinki Declaration, the ICH-GCP, the European Medical Device Directive 93/42/EEC and the ISO standard 14155 and ISO 14971 (where applicable), as well as the Swiss Human Research Ordinance and thus Swiss law.

The CEC receives an annual report and is informed about the course of studies.

2.6 Conflict

There is no financial conflict of interest on the part of the sponsor/investigator, nor is there a corresponding relationship of dependency.

SUPSI

2.7 Patient information and informed consent

The examiners will explain to each participant individually the nature of the study, its content, intent and objective. This includes the protocol flow, approximate time duration, possible risks and benefits. The participant is informed that participation is voluntary and can be withdrawn from the study at any time, without personal consequences of any kind. The participant will be informed about data protection, the handling of personal data and their access.

Each participant receives written subject information and the declaration of consent with the detailed study description and all necessary information to be able to decide whether to participate in the study. The participant will also be given sufficient time to read this written information and to ask questions to the responsible examiners.

The subject information and the informed consent form are submitted to the CEC, where they must be reviewed and approved.

The signed declaration of consent must be submitted before the start of the study process. The participant should read them before signing and check their contents. The responsible examiner then also signs the declaration of consent. Finally, the participant receives a copy of the declaration of consent. The signed declaration of consent is kept in the original as a study document in a locked filing cabinet.

2.8 Confidentiality & Privacy

The examiners ensure that the privacy of the participants is maintained. In particular, data protection and confidentiality are guaranteed, and no personal data is presented or published. The signed declaration of consent, as well as the completed questionnaire with the other personal details, are kept in the original as a study document in a locked filing cabinet.

The digital data is encrypted and treated confidentially, and access to the personal data is denied to third parties. The digital data collected is stored solely on the institute's own computers and is not passed on to any external persons or transferred to other computers.

Direct access to the personal data is allowed only to the head of the research laboratory (study leader), as well as authorized persons of the CEC.

2.9 Early termination of the study

The sponsor or the principal investigator or physician present may discontinue the study early if/for:

- ethical concerns
- insufficient number of subjects
- the safety of the participants cannot be guaranteed
- Findings from clinical practice make it pointless to continue the study
- early evidence or harm of the experimental intervention has been proven
- the health of the subjects is at risk

2.10 Adjustments to the protocol

Adjustments and changes to the current study are only permissible after review by the CEC.

Short-term changes to the protocol prior to an audit by the CEC may be made to ensure the rights and safety of participants. However, such adjustments must be documented and reported to the CEC as

SUPSI

soon as possible.

Significant changes are only permissible after a review of the CEC. Any other changes must be notified to the CEC as soon as possible and listed in the annual report.

SUPSI

3 BACKGROUND AND RATIONALE

3.1 Background and justification

Research has consistently shown that exposure to extreme environments (i.e., hot, cold, altitude) can impair cognitive function (Taylor et al., 2015). For logistical reasons and to better control the (climatic) conditions in which the subjects are tested, most of these tests are carried out in laboratories. By testing under such controlled conditions, researchers can remove any co-founding factors and isolate the cause of stress, allowing them to better understand the mechanisms by which impairment can occur. However, when exposed to such "real world" environments, they often experience a number of other additional stressors at the same time, which can also affect their performance. Surprisingly, however, little attention has been paid to the study of these additional stressors in combination (Tipton, 2012).

The best example of multiple stressors that occur in combination is when climbing to high altitudes. Although the percentage of oxygen remains constant at different altitudes (20.93%), the air pressure decreases exponentially as the altitude increases. As a result, the oxygen partial pressure in the arterial blood and tissues is reduced (hypoxia), which leads to a deterioration in both physical and cognitive performance. However, in addition to the stressful effects of hypoxia, other stressors, such as temperature and fatigue, can also be added, which are known to significantly affect human functions (McMorris et al., 2017).

The reduced oxygen level in the blood during exposure at high altitude causes breathing disorders during sleep. Consequently, sleep at altitude is characterized by a reduction in total sleep, sleep efficiency, and sleep quality (de Aquino Lemos et al., 2012).

While both hypoxia and sleep deprivation are reported to have negative effects on cognitive performance at rest, this may not be true when a person is exercising or moving. It is known that cognitive performance improves with normoxia with light moderate exercise (Chang et al., 2012). In addition, there is growing evidence that exercise can even cancel out the negative effects of hypoxia on cognitive performance (Ando et al., 2013; Komiyama et al., 2017). Another point that gives rise to further research in the field of hypoxia is the sensation of pain. It has already been shown in previous studies that the sensation of pain differs between normoxic and hypoxic situations (Noel-Jorand et al., 1996). To the knowledge of the authors, however, there are only limited studies that compare these parameters in a laboratory condition with the reactions in the real world. In addition, various patient groups also suffer from lung dysfunction (such as COPD) and are therefore at least partially under hypoxic conditions. With this study, we can contribute to understanding the psychophysiological reactions under hypoxia.

Aim of the study

The aim of this study is to evaluate and compare the psychophysiological changes during terrestrial and simulated altitude. These changes will be investigated after a 5-minute step-up task and after a 5-minute cold water immersion of the hand in a) a normobaric, normoxic situation, b) normobaric, hypoxic situation and c) hypoxic, hypobaric situation.

3.2 Medical product and indication

Simulated altitude training is quickly becoming the most promising development in the world in terms of athletic performance and peak fitness.

With the Cloud 9, a simulated altitude of 2700 m and 3530 m above sea level can be achieved. This corresponds to an oxygen partial pressure of 15.0% and 13.5% respectively. The Cloud 9 altitude training device is designed for all levels of sports (including athletes) who want to improve their performance. The Cloud 9 is a solid, certified product that complies with the European Directives on

SUPSI

Electromagnetic Compatibility, Machinery Directive, Air Pressure Equipment and Low Voltage Equipment (89/336/EEC, 91/368/CEE, 93/68/CEE, 97/23/EC, EN61010-1).

Cloud 9 mapping: <https://chasingtargets.eu/altitude-tent-rental-service/>

3.3 Preclinical evidence

Studies under hypoxic conditions have already been carried out in the medical field with a wide variety of pathologies, such as obesity under stress (Girard, Malatesta, & Millet, 2017; Park, Jung, Kim, & Lim, 2019) but also with seniors (Pransohler et al., 2017). Hypoxic conditions can lead to psychological changes in addition to physiological changes (Taylor et al., 2015). Chronic stays at altitude can further lead to a physiological change (Smith et al., 2014).

It is known that cognitive and physical performance improves with normoxia with light moderate exercise (Chang et al., 2012). In addition, there is growing evidence that exercise can even cancel out the negative effects of hypoxia on cognitive performance (Ando et al., 2013; Komiya et al., 2017).

SUPSI

3.4 Current clinical evidence

According to the authors' knowledge, there are currently hardly any clinical studies that contrast the psychophysiological effects of terrestrial altitude with simulated altitude.

3.5 Medical product: method of application in the study

During the normobaric, hypoxic situation, an altitude of 3530 m above sea level is simulated, which corresponds to an oxygen partial pressure of 13.5%. This situation is realized by a mask system, with the help of Cloud 9.

<https://trainingwithaltitude.co.uk/product/altitude-mask/>

3.6 Peers

The intervention group is also the control group, as a crossover design is used.

Randomization

Randomization takes place according to the situation (normobar & normoxic vs. normobar & hypoxic). The situation you find yourself in first is decided by drawing lots.

3.7 Risk / Benefits

Possible risks in the situation of terrestrial and simulated altitude are the appearance of headaches, impaired consciousness, disorientation and nausea. In addition, a doctor is present during the measurements. Subjects who may be at risk are recorded by the screening procedure and the health questionnaire and are not included in the study. However, the risk is to be classified as minor, as studies are already being conducted with obese patients and seniors under hypoxic conditions, which has not led to any complications. Participants do not derive direct benefits from participating in the study. More information on securing the test subjects can be found in chap. 8.1.1. Justification

SUPSI

for the choice of population

This series of studies is being conducted with healthy adults to minimize the health risk. The psychophysiological reactions of the body to terrestrial and simulated altitude training are assumed to be probable in this test subject population.

The test subjects are comprehensively informed about the course of the study and possible risks before they are accepted to participate in the study. You will also receive the information in written form and have the opportunity to ask questions if anything is unclear. The declaration of consent explains to them what their rights and obligations are when participating. In addition, they are informed that they may withdraw from participation at any time without giving reasons, without incurring any disadvantages as a result.

SUPSI

4 STUDY OBJECTIVES

4.1 General objectives

The aim of this study is to evaluate and compare the psychophysiological changes during terrestrial and simulated altitude. These changes will be investigated after a 5-minute step-up task and after a 5-minute cold water immersion of the hand in a) a normobaric, normoxic situation, b) normobaric, hypoxic situation and c) hypoxic, hypobaric situation.

4.2 Primary objectives

The primary goal is to compare and evaluate the physiological effects of terrestrial altitude and simulated altitude. For this purpose, the following parameters are measured:

Objective parameters:

- Perfusion of the skin microcirculation (flux)
- Blood oxygen saturation (%)
- Oxygen saturation of the muscles (%)
- Oxygen saturation of the brain (%)
- Heart rate (b/min)
- Blood pressure (mm/Hg)
- Skin temperature (°C)
- Lactate (mmol/l)
- Creatine kinase (U/L)
- Balance test (° & m/sec)

Subjective parameters:

- Pain sensation (N)

The primary goal is to compare and evaluate the psychological effects of terrestrial altitude and simulated altitude. For this purpose, the following parameters are measured:

Subjective parameters:

- Sleep Disorder Questionnaire
- Lake Louis Altitude Sickness Questionnaire
- Dyspnea questionnaire
- State of mind questionnaire
- Stanford Sleepiness Questionnaire
- Automated, cognitive test battery

4.3 Secondary Objectives

The secondary goal is to compare and evaluate thermal comfort and temperature perception according to terrestrial altitude and simulated altitude. For this purpose, the following parameters are measured:

-

Subjective parameters:

- Thermal comfort
- Temperature sensation

SUPSI

4.4 Other safety aspects (long-term)

No more risks than those discussed so far are to be expected in this study.

SUPSI

5 STUDENT OUTCOMES

5.1 Primary outcomes

Perfusion of skin microcirculation

The perfusion of the skin microcirculation is visualized using the Laser Speckle Contrast Imager (moorFLPI 2, moor instruments, www.moor.co.uk). The "moorFLPI-2 Full-Field Laser Perfusion Imager" measures blood flow measured in flow rates (arbitrary units) of the skin's microcirculation. The laser is intended for clinical and physiological research. The fabric is illuminated with a divergent infrared laser beam. The laser measures down to a depth of 1mm, so it mainly detects the superficial blood flow, speed and concentration of red blood cells. This measurement is measured during the baseline measurements, after the step-up task and up to 30 min after the cold water bath of the hand (5 min interval).

Oxygen saturation of the muscles and brain

The oxygen saturation of the muscles and brain is measured non-invasively with a deep tissue oxygenation monitor (moorVMS-NIRS, moor instruments, www.moor.co.uk). For this purpose, adhesive electrodes are attached over the muscle and forehead. This measurement is measured during the baseline measurements, after the step-up task and up to 30 min after the cold water bath of the hand (5 min interval).

Figure: Measurement of oxygen saturation of the brain and muscles

Oxygen saturation of the blood

The oxygen saturation of the blood is measured with a portable pulse oximeter with finger clip probe

SUPSI

(Nonin 7500, Nonin medical B.V., Plymouth, USA). This measurement is measured during the baseline measurements, after the step-up task and up to 30 min after the cold water bath of the hand (5 min interval).

Figure: Measurement of the oxygen content of the blood

Blood pressure and heart rate

The heart rate is measured with a heart rate belt and an additional 2-point ECG (Actiheart, Camntech Ltd., Cambridge, UK). Blood pressure is measured by means of an electronically automated upper arm blood pressure monitor (Boso-Medicus uno). This measurement is measured during the baseline measurements, after the step-up task and up to 30 min after the cold water bath of the hand (5 min interval).

Skin temperature

Skin temperature is measured via the iButton system (www.ibuttonlink.com). The self-adhesive sensors transmit the information about the skin temperature wirelessly to a computer. Furthermore, the skin temperature is recorded by means of a thermal imaging camera (FLIR). This measurement is measured during the baseline measurements, after the step-up task and up to 30 min after the cold water bath of the hand (5 min interval).

Lactate and creatine kinase

The lactate and creatine kinase measurement are carried out by capillary blood measurement (Accutrend, Roche Diagnostic, Rotkreuz, Switzerland & Reflotron, Roche Diagnostic, Rotkreuz, Switzerland). The affected area is disinfected and a superficial wound is pierced to take capillary blood. This measurement is measured during the baseline measurements, after the step-up task and up to 30 min after the cold water bath of the hand (5 min interval).

Balance measurement

The fluctuations of the hull are recorded and evaluated with the Sway Star™ System (www.b2i.info). The Sway Star™ is a measuring instrument that contains gyroscopes. It is attached to a belt that is placed around the patient's waist. The data is evaluated with the associated Sway Star™ software and transferred to the data sheet. This measurement is carried out after the baseline measurement and after the cold water bath immersion of the hand.

SUPSI

Figure: Measuring balance with the Sway Star™

Pain sensation

The pain threshold is measured using a pain pressure algometer (NOD, www.to-nod.com). As soon as the patient reports pain, this measurement is stopped. This measurement is carried out after the baseline measurement and after the cold water bath immersion of the hand.

Psychological measurements

The psychological measurements (sleep disorder, altitude sickness, dyspnea, state of mind, drowsiness) are evaluated on the basis of written questionnaires.

The cognitive test battery consists of 8 tasks (ANAM, US Department of Defence, Vista Life Sciences, USA), which are carried out on a laptop computer.

These measurements are carried out after the baseline measurement and after the cold water bath immersion of the hand.

5.2 Secondary outcomes

Thermal comfort and temperature perception

This parameter is measured using a scale. The test subjects indicate their subjective temperature perception on a 9-point scale from -4 (very cold) to +4 (very hot). They then rate the thermal comfort between 0 (pleasant) and 4 (extremely unpleasant) on a 5-point scale. These measurements are carried out after the baseline measurement and after the cold water bath immersion of the hand.

5.3 Security considerations

No further results are recorded that would serve safety.

Discontinuation of the experiment is the responsibility of the examiner with regard to the subject's subjective feelings and expressions.

If a test subject does not feel well during the application according to his or her subjective assessments, he or she can discontinue the experiment and withdraw participation in the study without any disadvantages. A doctor is also present to ensure the safety of the test subjects.

SUPSI

6 STUDIENDESIGN

Study design and justification

Randomized, clinical, crossover study

This is a category A intervention study (ClinO, Art. 20), whereby the intervention involves testing a tested product on healthy volunteers. The group size is $N = 24$. The intervention product (Cloud 9) is a solid, certified product that complies with the European Directives on Electromagnetic Compatibility, Machinery Directive, Air Pressure Equipment and Low Voltage Equipment (89/336/EEC, 91/368/CEE, 93/68/CEE, 97/23/EC, EN61010-1).

6.1 Method for minimizing influencing factors

6.1.1 Randomization

The situation (normobar & normoxic vs normobar & hypoxic) will be randomized. The randomization procedure is carried out by lottery.

6.1.2 Blinding

Blinding the test subjects is not possible with regard to the situation.

It is not possible to blind the data collectors.

However, blinding the statistician can be guaranteed, who has no access to the personal data of the test persons and is not present during the data collection.

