6.2 Procedure for unblinding (code break)

There is no provision for the statistician to be blinded.

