6.3 Procedure for unblinding (code break)

Blinding (coding) of study participants is only permitted if an unforeseen incident or medical problems occur during or after the completion of study participation in a subject, which may be attributable to participation in the study.

For incidents (AE) that occur during or shortly after the simulated altitude (within the first 24 hours) and can potentially be attributed to the intervention, the principal investigator may, at his or her discretion, immediately waive the blinding of the study participant and the investigators present to ensure adequate treatment of the study participant.

In the case of incidents (AE) that occur longer than 24 hours after the simulated altitude, clarification with a doctor is mandatory and a doctor's certificate is required for the lifting of blindness. Data may then also be passed on to the attending physician with the consent of the study participant concerned. This approach is justified because no life-threatening incidents are to be expected due to the intervention used here.

SUPSI

SUPSI

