11.4.4 Interim analyses

The data is processed after the project ends. No additional interim analyses are planned.

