12.4 Audits and inspections

A report on the current status of the study is given orally to the study supervisor ([name]) on a monthly basis. In addition, [name] will be present during the measurements. This also includes demonstrating and presenting results and statistical analyses.

An annual report on the course of the study will be submitted to the CEC. Authorized persons of the CEC can view the data forms as well as the digital data on the institute's own computers at any time.

Data protection is guaranteed at all times.

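### The statistician's blind that 6.1.2 calls guaranteed does not mask the situation, and 6.2, 6.3 and 12.4 need to be reconciled with it

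*Combined protocol and SAP*

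**What the plan says.** Section 6.1.2 deals with three parties. For participants: "Blinding the test subjects is not possible with regard to the situation". For examiners: "It is not possible to blind the data collectors". For the analyst: "However, blinding the statistician can be guaranteed, who has no access to the personal data of the test persons"; the same sentence adds that this person does not attend the data collection. Section 6.1.3 states that no further methods are used.

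Section 6.2, headed as a procedure for unblinding, consists of one sentence: "There is no provision for the statistician to be blinded".

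Section 6.3, under the same heading, lets the principal investigator lift the blind of the participant and of the investigators present after an event. The earlier of its two time windows begins "For incidents (AE) that occur during or shortly after the simulated altitude (within the first 24 hours"; the later one is also tied to simulated altitude. Section 10.3.1 defines an adverse event under simulated or terrestrial altitude.

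On timing, 11.4.2 places the analysis after data collection for the whole project is complete, and 11.4.4 says: "The data is processed after the project ends. No additional interim analyses are planned". Section 12.4 describes a monthly oral status report to the study supervisor, then someone's presence at the measurements, and then: "This also includes demonstrating and presenting results and statistical analyses".

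**The concern.** Examiners and participants both know the situation, and many outcomes are self-reported or depend on effort: questionnaires, pressure pain threshold, the cognitive battery, thermal ratings. The analyst's blind is the only one the plan claims. If it conceals identity but not situation, choices about exclusions, outliers and model details can be made with the comparison in view, while a reader of the report would believe they were not.

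The neighbouring sections add to the doubt. One appears to deny the blind. Another regulates the lifting of a blind that nobody holds. A third could put emerging results in front of the people who are still collecting data.

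**Working it through.** The plan gives no figure for this point, so the check is a comparison of sections, with one count.

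1. **What each support in 6.1.2 hides.** Having no access to personal data hides who a record belongs to. Being absent from data collection means not seeing sessions take place. Neither says anything about the column that marks a record as simulated, control or hut.

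2. **Whether masking is described elsewhere.** Section 1.7 codes identity and keeps that code from data processors. Sections 2.8, 12.2.2 and 12.5 concern encryption, anonymisation and access to personal data. Section 6.1.3 rules out further methods. Section 11.4.2 makes situation the first factor, so the analysis file must carry some indicator of it; whether that indicator is open or coded is not stated. Section 12.3 and part of the front matter were not in the text available to me, and I count nothing there as missing.

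3. **Whether simple recoding would be enough.** The schedule in 9.1 lists consent at 30 min, simulated altitude once, terrestrial altitude twice and control once, each session at 110 min: 30 + 110 + 2 × 110 + 110 = 470 min, which reproduces the plan's total. That is four sessions per person. With 24 completers there are 24 × 4 = 96 session records: 24 simulated, 24 control and 48 hut. A three-level code would show one level with twice as many records as either of the others, which identifies the hut at once. Four session-level codes with 24 records each remove that clue.

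4. **6.1.2 against 6.2.** Read literally they give opposite answers. The heading of 6.2 is about unblinding, however, and the first sentence of 6.3 makes sense only if blinding there means unblinding. Read the same way, 6.2 says that there is no provision to unblind the statistician, which agrees with 6.1.2.

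5. **6.3 against 6.1.2 and 10.3.1.** Section 6.3 waives a blind for two parties whom 6.1.2 declares impossible to blind. Both of its time windows refer to simulated altitude only, while 10.3.1 counts events under either exposure.

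6. **12.4 against 11.4.2 and 11.4.4.** It is unclear whether the sentence on results refers to the monthly report or to the presence at the measurements, and 12.4 gives no date. Table 1 ends data collection in October 2019 and places statistics in November and December 2019, so later reports could show analyses without breaching 11.4.2. The synopsis ends measurements in December 2020, and on that timeline such reports would fall within data collection. The conflict is conditional on timing, which 12.4 should state.

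**The case against.** The best case for the plan is that little here is a design decision. Section 6.2 is probably a wording slip, in a text with other signs of translation. Section 6.3 may partly refer to the identity code, since it writes of coding and of passing data to a treating physician. That reading fits poorly with investigators, who have no such code. I accept the slip in 6.2; it still needs correcting, because the current sentence denies the only blind claimed.

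Three stronger readings are tempting, and the documents do not support them.

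- *A reader might infer that the monthly reports defeat the analyst's blind.* Section 12.4 names the supervisor as recipient and does not say that the statistician gives or receives the report. It also leaves the timing open.
- *A reader might infer repeated significance testing with an inflated false-positive rate*, because 2.9 lists as a ground for stopping that "early evidence or harm of the experimental intervention has been proven". No section describes a monthly test, a threshold for stopping or a stopping decision based on one, and 11.4.4 rules out interim analyses. I therefore attach no error rate.
- *A reader might infer that events after the hut night are left without any rule.* Sections 10.3.1 and 10.3.3 provide for recording and reporting under both exposures, and nobody has a situation blind to break. The gap in 6.3 is an inconsistency of text with little practical effect.

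A further objection is that coding cannot fully blind the analyst: oxygen saturation may separate normoxia from hypoxia, and 11.4.2 compares named situations. This stands in part, and it is a reason either to state the limits of the blind or to stop calling it guaranteed.

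**Conclusion.** The point holds as a mismatch between claim and mechanism. Section 6.1.2 guarantees a blind, but its two supports do not mask the situation, and no available section supplies masking. The literal conflict with 6.2 is probably editorial. Section 6.3 is inconsistent with 6.1.2 and narrower than 10.3.1. Section 12.4 conflicts with 11.4.2 and 11.4.4 only if results are shown while data are still being collected; in that case unblinded examiners could be exposed to emerging results.

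No bias or error rate can be calculated from what the documents give. The conclusion assumes that the files excluded from the public text contain no masking procedure. The change should be made: the claim will be read as a safeguard, and correcting it costs little.

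**What to change.** - **6.1.2.** Give the statistician a dataset with four neutral session-level codes, without calendar dates, since two sessions on consecutive days would point to the hut. The study leader holds the key until the prespecified models are run and saved. So that the analyst need not be told which codes to contrast, the model can be run for every pair of codes (4 × 3 / 2 = 6) and the relevant pairs read off when the key is opened. State that oxygen saturation may partly reveal the situation. If this is not wanted, withdraw the word guaranteed and describe the analysis as unblinded.
- **6.2.** Reword to agree with 6.1.2.
- **12.4.** State when results may be presented. Before data lock, limit reports to recruitment, conduct, safety events and data completeness, with no results by situation.
- **6.3.** Reconcile with 6.1.2 and 10.3.1, so that it is clear whose blind or code is meant and which exposures are covered. The content of that rule is for the sponsor and investigator.

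The cost is protocol wording, recoding of the session identifier and a few extra model runs. The supervisor sees no results by situation until data lock.
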